## **METHODS**

The patients will be randomized into two groups by closed envelop randomization; group (A) will undergo cesarean section with bladder dissection and group (B) will undergo cesarean section without bladder dissection.

All patients will be subjected to the following:

- 1- Complete history taking (gynecological, obstetric, medical, surgical)
- 2- Cesarean section using Joel-Cohen incision :
  - Joel-Cohen skin incision(straight skin incision 3 cm below the line connecting the anterior superior iliac spines)
  - Blunt dissection of the subcutaneous layer
  - Blunt extension of the fascial opening
  - Blunt entry into the peritoneum
  - Sharp superficial then blunt entry into the uterus
  - Spontaneous removal of the placenta
  - Double layer closure of the uterus
  - Non-closure of the peritoneum
  - Continuous closure of the fascia
  - Continuous suture of the skin

Group (A) will be subjected to bladder flap dissection after blunt entry to peritoneum and before sharp entry to uterus, while group (B) will undergo traditional steps with sharp and blunt entry into uterus directly after blunt entry into peritoneum After 3 and 6 months all patients will be subjected to Two-dimensional trans vaginal ultrasound:

Women will be examined after emptying their bladder. The uterus and uterine scar will be examined in the mid sagittal plane. A niche is defined as an anechoic space at least 2 mm deep at the presumed site of the cesarean section scar.

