## PATIENTS

This study will be prospectively conducted on 250 women recruited from ElShatby university maternity hospital delivery ward; They will be randomized into two groups group (A) and group (B) by closed envelop randomization. Group (A) will undergo cesarean section with bladder dissection and group (B) will undergo cesarean section without bladder dissection.

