#### Methods of measurement according to modified Delphi procedure:

Endometrium should be ignored; niche measurements are based only on myometrium. Best method to obtain correct sagittal plane for niche measurement is by starting in mid-sagittal plane, with good visualization of cervical canal, then moving transvaginal probe laterally to both sides.

Best method to visualize niche in transverse plane is by starting in sagittal plane, keeping good visualization of niche while rotating transvaginal probe from sagittal to transverse plane.

Best method to detect possible branches is in transverse plane, screening entire lower uterine segment from cervix to corpus.

To measure uterine niche, there should be good visualization of lower uterine segment only; this applies to all uterine positions (anteversion, retroversion or stretched).

It is useful to vary pressure with transvaginal probe in order to achieve best plane for niche measurement.

For simple niches, all measurements can be done in a single plane, while, for complex niches, more than one plane may be necessary.

The length, depth and width of the niche should each be measured in the plane in which it is largest. The distances between the niche and the VV

fold, and the niche and the external os were considered not to provide additional value for basic niche evaluation.

RMT should be measured in the sagittal plane in which the main niche has the smallest RMT.If visible, branches should be measured; measurements of the depth and the RMT should be made separately for the main niche and including any branch.

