## **Outcome measures:**

- 1. Incidence of occurrence of cesarean scar (cs) niche in each group.
- 2. Correlation between the depth of niche and the residual myometrium in each group.
- 3. Comparison between the thicknesses of residual myometrium to adjacent normal myometrium in each group.
- 4. Complains of niche if present.

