## IV-Comparison between two groups as regard incidence of niche

Niche is defined as an anechoic space at least 2 mm depth at the presumed site of the caesarean section scar.

The incidence of niche was higher in group I, yet it did not reach statistical significance. (P=0.087). (Table 4, Fig. 17)

Table (4): Comparison between the two studied groups regarding incidence of niche

Incidence of niche	Group I		Group II		
	No %		No	%	
Absent	89	71.2	99	79.2	
Present	35	28.0	26	20.8	
X 	1.94				
P value	0.087				

Group I. cesarean section with bladder dissection Group II: cesarean section without bladder dissection  $X^2$  = Chi square-test p was significant if  $\leq 0.05$ 

[figure not shown]

Figure (17): Comparison between the two studied groups regarding incidence of niche

[figure not shown]

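### The methods describe no masking of the niche examiner, although the first-listed outcome is a yes/no ultrasound call at 2 mm that leaves the examiner some discretion

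*Protocol*

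**What the plan says.** The aim is to compare scar-defect incidence with and without bladder flap dissection. The first item under Outcome measures is "Incidence of occurrence of cesarean scar (cs) niche in each group"; no outcome is labelled primary.

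On assessment, the Methods say "After 3 and 6 months all patients will be subjected to Two-dimensional trans vaginal ultrasound", and then "A niche is defined as an anechoic space at least 2 mm deep at the presumed site of the cesarean section scar". The measurement section, based on a modified Delphi procedure, adds "It is useful to vary pressure with transvaginal probe in order to achieve best plane for niche measurement" and "The length, depth and width of the niche should each be measured in the plane in which it is largest".

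The only bias control described is at allocation: "The patients will be randomized into two groups by closed envelop randomization". Neither document says who scans, whether that person knows the arm, whether images are kept, or whether a second reader is used. Nor do they say whether the 3-month or the 6-month scan decides niche status.

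The SAP reports results. Table 4 gives 35 niches in group I (dissection) and 26 in group II (no dissection), with P=0.087, and describes the difference as not significant.

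**The concern.** The surgeon cannot be masked to bladder dissection. A person scanning three or six months later can be, and the Methods include no step to achieve it. Closed envelopes act at allocation and do nothing for assessment months afterwards.

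Three features make this more than a reporting gap:

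- **The outcome is a cut.** A small change in measured depth near 2 mm changes a woman's outcome from absent to present.
- **The examiner has discretion that bears on the cut.** Probe pressure and plane are chosen during the scan, and depth is the largest value found. A longer search can only raise it.
- **The protocol supplies an expectation.** Its section on adhesions names an unsutured bladder flap as a mechanism of impaired healing, and the Methods leave the peritoneum open in both arms. An examiner who knows the arm could reasonably expect more niches after dissection.

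At stake is how Table 4 is interpreted. If the examiner knew the arm, neither a difference nor its absence could be cleanly separated from expectation.

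**Working it through.** Masking has no sample-size figure of its own, so the check asks how many changed calls would alter the conclusion.

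**Inputs (SAP Table 4).** Group I: 35 present, 89 absent. Group II: 26 present, 99 absent. The group I counts sum to 124, but the printed 28.0% is 35/125, so both denominators are used. The threshold is 0.05; the SAP does not state sidedness, and two-sided is assumed here.

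**Formula.** For a table with cells a, b in group I and c, d in group II and total N, Pearson X² = N(ad − bc)² / [(a+b)(c+d)(a+c)(b+d)].

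**The reported result first.**
- 35/124 v 26/125: ad − bc = 35×99 − 89×26 = 1151. X² = 249×1151² / (124×125×61×188) = 1.86, two-sided P=0.173.
- 35/125 v 26/125: X² = 1.76, P=0.185.
- The SAP prints X²=1.94 and P=0.087. Neither denominator gives 1.94, and 1.94 would itself imply a two-sided P of about 0.164. The printed 0.087 matches half of 0.173. This mismatch is a separate matter; the steps below use the recomputed values.

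**Observed difference.** 35/125 − 26/125 = 9/125 = 7.2 points, 95% CI −3.4 to 17.8.

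**Calls needed to cross 0.05.** For 40/124 v 26/125, ad − bc = 40×99 − 84×26 = 1776, and X² = 249×1776² / (124×125×66×183) = 4.20. The other rows follow in the same way.

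| Scenario | Counts | Pearson P | Fisher P | Yates P |
|---|---|---|---|---|
| 5 more in group I | 40/124 v 26/125 | 0.041 | 0.045 | 0.057 |
| 5 more in group I | 40/125 v 26/125 | 0.045 | 0.062 | 0.062 |
| 6 more in group I | 41/125 v 26/125 | 0.032 | 0.045 | 0.046 |
| 5 fewer in group II | 35/125 v 21/125 | 0.034 | 0.048 | 0.049 |
| 3 more in I and 3 fewer in II | 38/125 v 23/125 | 0.027 | 0.039 | 0.039 |

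Five added calls in group I cross the line by Pearson with either denominator, but not by Yates with either and not by Fisher with 125. With 125, six cross it by all three tests. Five calls are 5/89 = 5.6% of the group I women read as niche-free.

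**Calls needed to remove the difference.** Five fewer in group I (30/125 v 26/125) leave 4/125 = 3.2 points, P=0.54. Equality (26 v 26) takes 35 − 26 = 9 net calls, or 9/125 = 7.2% of an arm.

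**Error shared by both arms.** Five over-calls in each arm (40/124 v 31/125) give P=0.19, close to the observed 0.173. Only arm-related error has the effect shown in the table.

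**The case against.** The strongest reply is that silence does not establish an unmasked scan. The protocol never says the examiner knew the arm, and nothing in the SAP shows arm-related error. The tipping counts also need errors that run in one direction. Both points stand, and they limit the conclusion to an exposure.

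A second reply is that the measurement section reduces discretion: it fixes the starting plane, excludes the endometrium and sets rules for which plane is measured, equally in both arms. That deserves credit and should lower measurement variability. It does not conceal the arm, and pressure and plane remain the examiner's choice.

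Three stronger readings are tempting but unsupported:

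- **That a handful of calls could erase the difference as easily as create significance.** Full removal takes nine net calls. The reported incidence result is also already non-significant, so there is no significant finding to erase.
- **That a known share of women lay close to 2 mm.** The smallest depths in Table 5 are 0.21 and 0.20 cm, which invites fitting a curve to its means and SDs. Table 5 covers only women already called positive, who could only be called down. No depths are given for women read as niche-free, the source of any extra positive calls. The fits also disagree. A gamma curve starting at 0.20 cm has shape ((0.331 − 0.20)/0.15)² = 0.76 in group I and puts about 12% of depths below 0.21 cm, the reported minimum. No such percentage should be quoted.
- **That Table 4 is biased.** The documents show a route for bias, not its occurrence.

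Finally, new Methods text cannot alter a trial that already has results. That is correct, and the fix treats the completed trial separately.

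**Conclusion.** The concern holds in a limited form. No masking of the niche examiner is described in the Methods or the measurement section, and the outcome that matches the stated aim is a threshold call with room for examiner influence. About five to six arm-related changes in one arm would carry the comparison across two-sided 0.05, the exact number depending on the test and on the 124 or 125 denominator. About nine net changes would bring the arms level.

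This rests on two assumptions: that errors, if any, ran in a direction related to arm, and that the test is two-sided. If the halved P-value that matches the printed 0.087 was intended, three added calls would do (38/124 v 26/125: 0.0755/2 = 0.038). How many women were close enough to 2 mm for their call to change is unknown. The gap should be corrected because the remedy is cheap and protects the main comparison; it does not show that the reported result is wrong.

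**What to change.** **Protocol, Methods.** Add that:

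1. the scan request carries only a study number;
2. the scan is done by someone who did not perform that woman's section and has no access to the operative note;
3. niche status and all measurements are recorded before allocation is revealed.

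The cost is protocol wording, a coded request form and some scheduling so that no one scans a woman on whom they operated. This assumes that more than one trained examiner is already available, which the documents do not say.

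**Completed trial.** Report whether the examiner knew the arm at each scan. If so, state the limitation beside SAP Table 4 with the tipping-point counts above. Re-measure without arm labels only if images were stored; the documents do not mention stored images. Disclosure costs a few sentences, and re-measurement, where possible, costs reader time but no new scans.

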#### Methods of measurement according to modified Delphi procedure:

Endometrium should be ignored; niche measurements are based only on myometrium. Best method to obtain correct sagittal plane for niche measurement is by starting in mid-sagittal plane, with good visualization of cervical canal, then moving transvaginal probe laterally to both sides.

Best method to visualize niche in transverse plane is by starting in sagittal plane, keeping good visualization of niche while rotating transvaginal probe from sagittal to transverse plane.

Best method to detect possible branches is in transverse plane, screening entire lower uterine segment from cervix to corpus.

To measure uterine niche, there should be good visualization of lower uterine segment only; this applies to all uterine positions (anteversion, retroversion or stretched).

It is useful to vary pressure with transvaginal probe in order to achieve best plane for niche measurement.

For simple niches, all measurements can be done in a single plane, while, for complex niches, more than one plane may be necessary.

The length, depth and width of the niche should each be measured in the plane in which it is largest. The distances between the niche and the VV

fold, and the niche and the external os were considered not to provide additional value for basic niche evaluation.

RMT should be measured in the sagittal plane in which the main niche has the smallest RMT.If visible, branches should be measured; measurements of the depth and the RMT should be made separately for the main niche and including any branch.

## **Outcome measures:**

- 1. Incidence of occurrence of cesarean scar (cs) niche in each group.
- 2. Correlation between the depth of niche and the residual myometrium in each group.
- 3. Comparison between the thicknesses of residual myometrium to adjacent normal myometrium in each group.
- 4. Complains of niche if present.

## **ETHICS OF RESEARCH**

## Research on human or human products:

 $\checkmark$  Prospective study: Informed consent will be taken from patients. In case of incompetent patients, the informed consent will be taken from the guardians.

Retrospective study: Confidentiality of records will be considered.

DNA / genomic material: Informed consent for DNA / genomic test and for research will be taken from patients. No further tests will be carried out except with further approval of committee and patients. If the samples will travel outside Egypt the researcher will be responsible for transportation and security approval.

All drugs used in the research are approved by the Egyptian Ministry of Health.

## **Research on animal:**

The animal species are appropriate for the test.

After test, if the animal will suffer, it will be euthanized and properly disposed.

After operation, it will have a proper postoperative care.

سأقوم بتسليم الموافقات المبنية على علم المريض الخاصة بالدراسة عند الانتهاء منها أو عند طلبها من اللجنة

# **RESULTS**

The results will be tabulated and statistically analyzed, using the standard statistical methods.

## DISCUSSION

The results will be discussed in view of achievement of the aim and will be compared with available literature and published data.

# RESULTS

This study was prospectively conducted on 250 women recruited from ElShatby university maternity hospital delivery ward; they were randomized into two groups group (A) and group (B) by closed envelop randomization.

Group (A) was undergo cesarean section with bladder dissection.

Group (B) was undergo cesarean section without bladder dissection.

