### II-Comparison between two groups as regard obstetric history

Gravidity in group I had mean value  $1.44\pm1.03$  and in group II had mean value  $1.312\pm0.737$ . Parity in group I had mean value  $0.136\pm0.68$  and in group II had mean value  $0.192\pm0.73$ . It was found that most of cases had no abortion in two studied groups 97(77.6%) and 99(79.2%) respectively. No ectopic cases was higher with 125(100%) and 124(99.2%) respectively. Gestational age had mean value  $37.41\pm2.37$  and in group II had mean value  $36.99\pm2.50$ .

[figure not shown]
There were no statistically significant differences between the two studied groups regarding gravidity (P = 0.133), parity (P = 0.069), abortion (P=0.465), ectopic (P=0.159) and gestational age (P = 0.175). (Table 2, Fig. 15)

[figure not shown]
Obstetric history	Group I	Group II	T test P value
Gravidity			
Range	1-9	1-6	0.133
Mean	1.44	1.312	0.155
SD	1.03	0.77	
Parity			
Range	0-6	0-4	0.069
Mean	0.142	0.192	0.009
SD	0.68	0.73	
Abortion			
No	97 (77.6%)	99 (79.2%)	0.465
1-2	27 (21.6%)	23 (18.4%)	0.403
>2	1 (0.8%)	3 (2.4%)	
Ectopic			
No	125(100.0%)	124 (99.2%)	0.159
Yes	0.0 (0.0%)	1 (0.8%)	
Gestational age			0.175

[figure not shown]
Table (2): Comparison between the two studied groups regarding obstetric history.

Range	34-41	33-41	
Mean	37.41	36.99	
SD	2.37	2.50	

Group I. cesarean section with bladder dissectiont-test = student t-testGroup II: cesarean section without bladder dissection p was significant if  $\leq 0.05$ 

[figure not shown]

Figure (15): Comparison between the two studied groups regarding obstetric history.

[figure not shown]

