#### III-Comparison between two groups as regard uterine position

AVF position in both groups was higher 108(86.4%) and 116(92.8%) respectively followed by RVF position with 15(12%) and 8(6.4%) respectively, erect position was equal in both groups with 1(0.8%). There was statistical significant increase in group I than group II regarding the RVF position (P=0.03). (Table 3, Fig. 16)

Table (3): Comparison between the two studied groups regarding the uterus position.

Uterus	Group I		Gro	up II	P value
position	No	%	No	%	
AVF	109	87.2	116	92.8	0.265
RVF	15	12.0	8	6.4	0.03*
Erect	1	0.8	1	0.8	1.0

Group I. cesarean section with bladder dissection Group II: cesarean section without bladder dissection  $X^2$  = Chi square-test p was significant if  $\leq 0.05$ \* = Significant at level 0.05

**Figure (16):** Comparison between the two studied groups regarding the uterus position.

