# VI- Comparison between the two groups regarding post delivery complain

[figure not shown]
The incidence of post-delivery complaint (HMB, Intermenstrual spotting and post coital bleeding) after 6 months was more in group I than group II, but it did not reach statistical significance. The most common complaint was spotting 8(61.5%) v.s 4(50%) followed by post coital bleeding 3(23.1%) v.s 2(25%).

So ,There was no statistical significant difference between two studied groups regarding post-delivery complain (P= 0.621, 0.102)

Post delivery complain	Gro	Group I		up II	P value
	No	%	No	%	
No	112	89.6	117	93.6	0.621
Yes	13	10.4	8	6.4	0.102
Spotting	8	61.5	4	50.0	0.071
НМВ	2	15.4	2	25.0	1.0
Post coital bleeding	3	23.1	2	25.0	0.92

Table (6): Post delivery complain in the two studied groups.

Group I. cesarean section with bladder dissection Group II: cesarean section without bladder dissection  $X^2$  = Chi square-test p was significant if  $\leq 0.05$ 

[figure not shown]

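### Table 4 classifies 124 group I women for niche but takes percentages over 125, and neither document gives the numbers scanned at 3 or 6 months

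*SAP*

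**What the plan says.** The Protocol, under PATIENTS, plans the trial size: "This study will be prospectively conducted on 250 women recruited from ElShatby university maternity hospital delivery ward". Under METHODS it sets the follow-up: "After 3 and 6 months all patients will be subjected to Two-dimensional trans vaginal ultrasound". The SAP's RESULTS section reports the same total: "This study was prospectively conducted on 250 women recruited from ElShatby university maternity hospital delivery ward; they were randomized into two groups".

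The arm size of 125 appears in the obstetric history section: "No ectopic cases was higher with 125(100%) and 124(99.2%) respectively".

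Table 4 (section IV, incidence of niche) has these two rows, with group I first:
- "Absent 89 71.2 99 79.2"
- "Present 35 28.0 26 20.8"

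The uterine-position text (section III) reads: "AVF position in both groups was higher 108(86.4%) and 116(92.8%) respectively followed by RVF position with 15(12%) and 8(6.4%) respectively". It adds one woman per arm with an erect uterus. Table 3 in the same section gives 109 instead of 108 anteverted women in group I.

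Section VI reports complaints at six months: "The incidence of post-delivery complaint (HMB, Intermenstrual spotting and post coital bleeding) after 6 months was more in group I than group II". Its Table 6 gives every woman in both arms a complaint status.

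Neither document states how many women attended the 3-month or the 6-month scan, how a missed scan is handled, or which of the two scans Table 4 reports.

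**The concern.** Niche is an imaging outcome measured months after randomisation, in women recruited on a delivery ward who must come back for it. A woman who is not scanned has no niche result. If she stays in the denominator, she is scored as niche-free without having been examined, which understates incidence in her arm. If such women are more numerous in one arm, the difference between arms shifts as well.

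Table 4 shows this pattern for one group I woman: she is missing from the counts but present in the denominator. Because the numbers scanned are not given, a reader cannot tell whether she is a single slip or whether other unscanned women sit among those counted as niche-absent. At stake are the accuracy of the main incidence figure and the reader's ability to judge how far the non-significant comparison depends on missing scans.

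**Working it through.** **1. Counts and denominators, group I**

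| Source (SAP) | Sum of counts | Base of the percentages |
|---|---|---|
| Section III text, uterine position | 108 + 15 + 1 = 124 | 108/125 = 86.4%, so 125 |
| Table 3, uterine position | 109 + 15 + 1 = 125 | 109/125 = 87.2%, so 125 |
| Table 4, niche | 89 + 35 = 124 | 89/125 = 71.2% and 35/125 = 28.0%, so 125; sum 99.2% |
| Table 6, complaints | 112 + 13 = 125 | 112/125 = 89.6%, so 125 |

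Group II is complete where checked: 116 + 8 + 1 = 125, 99 + 26 = 125 and 117 + 8 = 125.

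**2. The printed test.** Table 4 gives chi-square 1.94 and P = 0.087. Pearson chi-square without continuity correction, two-sided, against 26/125 in group II:
- 35/124 (printed counts): chi-square 1.86, P = 0.173
- 35/125 (missing woman set to absent): 1.76, P = 0.185
- 36/125 (missing woman set to present): 2.15, P = 0.143

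None gives 1.94, and 1.94 itself corresponds to a two-sided P of 0.164. The printed 0.087 equals half the two-sided P on 35/124 (0.0866). On 35/125 half would be 0.0925. So the test may have been run one-sided on 124 women while the percentages used 125, but the documents do not say so.

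**3. Effect of the one woman.** On the women classified, incidence in group I is 35/124 = 28.2%, against 28.0% printed. Her two possible results bound P at 0.143 and 0.185. Neither is near 0.05.

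**4. How many such women would be needed.** Suppose k unscanned group I women were counted as niche-free but had a niche. Group I becomes (35 + k)/124 or (35 + k)/125, against 26/125:

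| k | Pearson P, n = 124 | Pearson P, n = 125 | Yates P, n = 124 | Yates P, n = 125 |
|---|---|---|---|---|
| 4 | 0.056 | 0.061 | 0.077 | 0.084 |
| 5 | 0.041 | 0.045 | 0.057 | 0.062 |
| 6 | 0.029 | 0.032 | 0.041 | 0.046 |

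Fisher's exact test at k = 5 gives 0.045 on 124 and 0.062 on 125.

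If unscanned women are instead only removed from the niche-absent count, and all are in group I, the crossing point is 35/109 v 26/125 (P = 0.049). That means removing 15 women from 124, or 16 from 125.

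**5. Loss in both arms.** The loss rate is not given. Assuming 5% to 15%, it is 0.05 × 125 ≈ 6 to 0.15 × 125 ≈ 19 women per arm. Removing equal numbers from the niche-absent count of both arms gives:
- 12 per arm: 35/113 v 26/113, P = 0.18
- 19 per arm: 35/106 v 26/106, P = 0.17

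A full best/worst-case bound with six per arm would run from 41/125 v 26/125 (P = 0.032) to 35/125 v 32/125 (P = 0.67).

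**The case against.** The strongest reply is that this is a clerical slip. Table 3 places all 125 group I women in a uterine position, so the 108 in the text may be a typing error, and 89 in Table 4 may be one too. The chapter has other small mismatches, such as the group I parity mean (0.136 in the text, 0.142 in Table 2). Table 6 does not settle the matter either, since a woman can be asked about complaints without being scanned. This objection stands as far as it goes: the documents cannot tell a misprint from a missing scan. Either way Table 4 needs correcting, and only the scan records can show how.

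A reader might go further and make any of these inferences, which the documents do not support:
- **All 250 women completed six months.** No sentence says so. The RESULTS section says recruited and randomised; complete follow-up is read off the denominators, and Table 4 as printed contradicts it for one woman.
- **Women who did not return were replaced to keep 125 per arm.** Nothing in either document indicates replacement.
- **The handling of absentees must be one of a short list: no loss, replacement, or scoring as negative.** A woman seen only at 3 months could have been counted on that scan, because Table 4 names no visit.
- **Four women would overturn the result.** Four group I reclassifications leave P at 0.056 to 0.061. Four fewer niches in group II gives P = 0.046 on 124, but that requires women recorded with a niche to lose it, which non-attendance does not produce.

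**Conclusion.** The point holds as a defect in the denominator and in the reporting of the main outcome. Table 4 counts 124 group I women and divides by 125, the uterine-position text is short by one in the same arm, and the numbers scanned by arm and visit are not given.

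The known error is small: 28.0% against 28.2%, with two-sided Pearson P between 0.14 and 0.19 whatever the woman's result. If she is the only one missing, the non-significant conclusion holds.

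A larger effect is possible but conditional. The smallest reclassification that crosses 0.05 is about five unscanned women, all in group I, all counted as niche-free and all with a niche, tested without continuity correction. With Yates' correction it takes six. Removing niche-absent women from group I alone takes 15 or 16. Balanced removal leaves P at about 0.17 to 0.18. These figures rest on Table 4's other counts being right and on a two-sided test. The documents neither show nor exclude losses of that kind.

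**What to change.** 1. Trace the group I woman in the scan records, establish whether she was scanned, and treat her consistently in Tables 3, 4 and 6 and in the section III text. If the count is a misprint, correct it.
2. Use the women actually scanned as the denominator for niche and uterine position, and the women actually asked for complaints, by arm, and name the visit. If 124 is right, report 35/124 (28.2%) v 26/125 (20.8%), two-sided Pearson P = 0.173. Correct the printed chi-square and P to match, and state that the test is two-sided.
3. State the numbers randomised, scanned at 3 months and scanned at 6 months in each arm. Beside the niche comparison, add a best/worst-case bound over all randomised women: unscanned women set to niche present in group I and absent in group II, then the reverse.

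The cost is a re-tabulation from existing allocation and scan records plus one sensitivity analysis, with no new patients or scans. The downside is that the stated 125 per arm may fall slightly. If everyone was scanned, one sentence and a corrected Table 4, Table 3 and section III text settle the point.
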